At the end of this 30 minutes, if the participant would like to complete the first set of questionnaires while he/she is in clinic, he/she will answer the questions on a tablet (or paper if the patient prefers) about his/her quality of life, pain and bladder management. These questionnaires should take about 10 minutes to complete. If the participant does not have the time at the current clinic visit to complete these questions, a link will be emailed to the participant, which when clicked, will take the participant to the Assessment Center, where the questionnaires will be completed. For participants who don't have a computer, who are not able to use a computer or prefer to have the questions read to them, study personnel will set up a time to call and the questions will be completed over the phone.

The patient will be asked to complete the same questionnaires that were completed at baseline, every 3 months for up to 1 year. This will be accomplished by either 1) sending the participant the questionnaire link via email 2) calling the participant and completing the questionnaire via phone 3) approaching the participant at his/her next standard of care clinic visit (if this visit falls within the 3 month window) to see if he/she would like to complete the next set of questionnaires either by paper or table. Also, there is an Exit Interview that will be given when the participant finishes the study. This Exit Interview can be sent to the participant via email with a link to the questions, or the participant can do the Exit Interview over the phone with study personnel; whichever method the participant prefers. The Exit Interview asks questions about any changes over the past year in bladder management, any surgeries that might have affected bladder management and any complications that resulted in a change of bladder management for the participants. The Exit Interview questions will take approximately 15 to 20 minutes to complete.

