Data from participants that meet the study criteria and are enrolled in the study will be collected for research purposes only. A participant list will be placed on an excel spread sheet that will be stored in a secure folder on a secure drive. Access to this secure folder is only granted by the IT department upon request by the Research Manager. The excel database will contain the following information: Patient full name, medical record number, phone number, email, where consent was obtained, date of consent, date the questionnaires were sent, date questionnaires were completed and target date of future questionnaires. Data from the baseline assessment will be stored in REDCap and will include the participant's full name, address, phone number, medical record number, date of birth, email address, date of injury, previous medical history information, and current medical history information.

For the questionnaires done at baseline and then again every 3 months, the participants are sent a link, which is generated upon study enrollment with a unique participant identification number and is specific to each individual participant. The questionnaire link is sent to the participant via email, which takes them to the Assessment Center where the questionnaires are completed. Some participants will have difficulty completing these questionnaires themselves either because they don't have access to a computer or because of physical limitations. For these participants, study personnel will call them and read the questions to them over the phone.

can only be assessed via the link that is sent to the participants, and no PHI is collected for the questionnaires at the Assessment Center. The participants are identified by their unique study ID only.

Termination of the project is contingent upon data analysis and manuscript preparation which should be completed in six years.

The University of Utah IRB will review this protocol and any modifications.

Procedures performed for research purposes only:

Statistical Methods, Data Analysis and Interpretation

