our primary analysis for aims 1-3 is to summarize patient experiences over the 12month period, defined by his/her treatment at enrollment (i.e., ignoring any changes in treatment). A secondary analysis for aims 1-3 will be to allow treatment group to be time varying for the 10-15% who are expected to change treatment during the course of the study. This latter type of analysis provides a more general characterization of QoL by treatment type, but it is limited in that it is more difficult to adjust for covariates -- more details are provided below.

Primary Analysis for Aims 1-2:

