Our primary endpoints for aims 1 and 2 are the average of total QoL scores over time (total Neuro-QoL score and total NBSS score, respectively). For our primary analysis, these outcomes will be analyzed in a linear mixed effects regression framework, and our primary predictor variable will be the patient's baseline treatment type. Thus, even if a patient switches treatment during our study, we will ignore this change here and consider any change in OoL to just be part of a patient's typical one year experience starting from treatment X. Given that there are only five time points, it should be feasible to model within patient correlations using an unstructured covariance matrix. In these models we will evaluate the three possible pair-wise contrasts: CIC vs. IDC, CIC vs. Surgery and IDC vs. Surgery for statistical significance at the 0.017 Bonferroni-adjusted significance level. Key covariates that will be included in the aim 1-2 models are: time since injury at baseline (coded as a categorical variable with levels <1 year, 1-5 years, and >5 years), physical limitations severity (mild, moderate severe), time on bladder management strategy recorded at baseline (<6 months, 6m-1.5 years, >1.5 years), age at baseline (coded as <20, 20-30, 30-40, 40-50, >50), sex, follow-up time point and BMI. In addition, we hypothesize that interaction effects exist between treatment group at baseline and time on baseline treatment, time since injury, injury severity and patient age. This is because different treatments may have different complication rates, and longer times on a particular treatment may differ from shorter times on the treatment in terms of QoL. Similarly, patient satisfaction (and thus potentially QoL) with treatment type may vary with patient age, time since injury and injury severity. The possibility of additional pair wise interactions between treatment group and the covariates will be investigated in an exploratory fashion. Stata v.12 software will be used to extract the marginal coefficients, 95% confidence intervals (CIs) and p-values for each treatment group contrast in the presence of these interactions using the "margins" command (http://www.stata.com/stata11/margins.html). To summarize patient outcomes by treatment group, we will provide average QoL estimates and 95% CIs for some combinations of treatment group, treatment duration, time since injury, injury severity and age subcategories. While this corresponds to $3^{5}=243$ possible different subcategory combinations, these descriptive results will be estimated from our model based on the full available sample size. Thus these results will provide a profile of expected outcomes for each treatment group given different combinations of patient and injury characteristics.

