For our tertiary aim of evaluating cumulative complication rates (categorized as 0, 1-3, 3-5, >5) by treatment group on QoL, we will adopt a similar modeling framework as described for Aims 1-2, except that complications will be included in the model along with its interaction with treatment group. We will use a likelihood ratio test to evaluate the statistical significance of this interaction term, i.e. to answer our main question of whether or not the relationship between cumulative complications and QoL differs by treatment group. We will also provide average QoL estimates and 95% CIs for combinations of subcategories of complications, treatment group, treatment duration, time since injury, and age using Stata's margins command. We will also plan to implement the Aims 1-2 secondary analysis where treatment group is modeled as a time varying predictor. Again these models will include the additional interaction term between treatment group and cumulative complications.

While our original analysis for our PCORI grant funding specified data collection for 12 months follow-up, any additional longitudinal data follow-up would be useful and novel data for the field and will be collected as available.

A Note on Missing Data

One benefit of the mixed effects modeling framework is that our models will include all available patients even if a patient has a missing value for one or more time points. However, missing data is likely, and we will plan to use multiple imputation (MI) to investigate the sensitivity of our results to missing data (36, 37).

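### Multiple imputation is the only planned check on missing data and, with no departure term, makes the mixed model's missing-at-random assumption; one delta-adjusted analysis should be pre-specified.

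*Combined protocol and SAP*

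**What the plan says.** The section A Note on Missing Data is the only missing-data plan in the combined protocol and SAP. It notes that "our models will include all available patients even if a patient has a missing value for one or more time points", accepts that some data will probably be missing, and then says "we will plan to use multiple imputation (MI) to investigate the sensitivity of our results to missing data", with two general references on imputation. It gives no missingness assumption, imputation model, auxiliary variables or departure parameter.

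The primary analysis is a linear mixed model. The Analysis Plan Overview says that the goal of "our primary analysis for aims 1-3 is to summarize patient experiences over the 12month period", grouped by treatment at enrolment. Under Primary Analysis for Aims 1-2, "Our primary endpoints for aims 1 and 2 are the average of total QoL scores over time". With five time points, the plan considers that "it should be feasible to model within patient correlations using an unstructured covariance matrix". The three pairwise contrasts are tested "for statistical significance at the 0.017 Bonferroni-adjusted significance level".

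On data collection, Procedures states: "The patient will be asked to complete the same questionnaires that were completed at baseline, every 3 months for up to 1 year". Completion may be by email link, phone, paper or in clinic. The tracking file holds "date the questionnaires were sent, date questionnaires were completed and target date of future questionnaires".

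**The concern.** A sensitivity analysis is informative when it relaxes an assumption that the main analysis needs. The mixed model needs scores to be missing at random: given the observed scores and covariates, whether a questionnaire is returned does not depend on the score it would have shown. Standard imputation, with nothing added, needs the same. If patients stop answering because they have got worse, or better, and do so at different rates or to different degrees across the three groups, both analyses move together.

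The endpoint averages over all five visits, so unreturned questionnaires are part of what is estimated. This matters for a descriptive association as much as for a causal effect. The plan itself expects complication rates and satisfaction to differ by treatment, so group-specific reasons for non-response are plausible, though not shown. What is at stake is a report that cites agreement between the two analyses as reassurance on a question that neither addresses.

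**Working it through.** **Figures in the plan.** There is no missing-data figure to reproduce. The test level is 0.05/3 = 0.0167, printed as 0.017; two-sided z = 2.387.

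**Inputs from the documents.** Five time points; 1,500 patients (background text) or 4,200 to 4,400 (Study Population; 4,300 used).

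**Inputs assumed.** Equal thirds (500 or 1,433 per group), SD 1, exchangeable correlation 0.7, dropout without return at a constant hazard h per follow-up visit, no covariates, full-data difference 0. Unseen scores lie d SD from what missing at random predicts.

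**1. Share of visits missing.** At visit k = 0,…,4 the missing fraction is 1 − (1 − h)^k; f is its mean over the five visits.
- Lighter case, h = 5.43% vs 2.60%: 20% vs 10% missing at month 12; f = 10.3% vs 5.1%, a gap of 5.2 points.
- Heavier case, h = 12% vs 6%: 1 − 0.88⁴ = 40% vs 1 − 0.94⁴ = 22% missing at month 12; f = 21.3% vs 11.3%, a gap of 10.0 points.

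**2. Bias of the contrast.** Bias = fA·dA − fB·dB. With a common shift:
- Lighter: 0.052 × 0.3 = 0.016 SD; 0.052 × 0.5 = 0.026 SD.
- Heavier: 0.100 × 0.3 = 0.030 SD; 0.100 × 0.5 = 0.050 SD.
- Equal missingness and equal shifts: zero.

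**3. Standard error and rejection of a true null.** Group information is n times the sum, over dropout patterns, of pattern probability times the inverse covariance of the visits seen. Inverting it, averaging over the five visits and adding the two groups gives SE². Rejection = Φ(bias/SE − 2.387) + Φ(−bias/SE − 2.387).

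| Missing at month 12 | Patients | SE | d = 0.3 | d = 0.5 |
|---|---|---|---|---|
| 20% vs 10% | 4,300 | 0.0329 | 3.0% | 5.6% |
| 20% vs 10% | 1,500 | 0.0556 | 2.1% | 3.0% |
| 40% vs 22% | 4,300 | 0.0333 | 6.9% | 18.8% |
| 40% vs 22% | 1,500 | 0.0564 | 3.4% | 6.7% |

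The nominal rate is 1.7%. Simulating the mixed model in the heavier case (4,000 replicates) gave 6.0% and 18.1% at 4,300, and 3.3% and 5.7% at 1,500. The bias does not shrink with sample size, so it weighs more at the larger one.

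**4. Do the two planned analyses move together?** This simulation had 500 per group, SD 10, correlation 0.7, a true difference of 0 and 150 replicates. Dropout was random in one group; in the other its log-odds rose by 1.0 per SD fall in the unseen score. Contrasts are in points:

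| Missing at month 12 | Full data | Mixed model | Standard imputation |
|---|---|---|---|
| 10–14% | 0.037 | 0.233 | 0.233 |
| 19–25% | −0.011 | 0.362 | 0.360 |
| 28–35% | 0.005 | 0.530 | 0.531 |

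Across these and three runs at log-odds 0.5, the two methods agreed within 0.003 points while both were biased. The delta that would have removed the bias was about 1.3 to 2.8 points, or 0.13 to 0.28 SD.

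**5. What a tipping point would show.** Shift one group only and treat the SE as unchanged: tipping shift = (observed contrast − 2.387 × SE)/f.
- Heavier case, 4,300 patients, threshold 0.0795 SD: a contrast of 0.10 SD tips at (0.10 − 0.0795)/0.213 = 0.10 SD; one of 0.20 SD tips at 0.57 SD.
- Heavier case, 1,500 patients, threshold 0.1345 SD: contrasts of 0.15 and 0.25 SD tip at 0.07 and 0.54 SD.

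The first contrast in each pair is fragile. The second survives shifts of up to more than half an SD.

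**The case against.** **The plan does not say missing at random.** This is correct, and a reader might wrongly infer that it does, or that imputation always requires it. Neither holds. The point is conditional: nothing in the text adds a departure term, and without one the method named is a missing-at-random method.

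**Imputation may rest on a weaker assumption than the mixed model.** This also stands. The study collects complications, treatment changes and an exit interview covering the year. Imputing with these could recover part of an unseen decline that tracks such events, and imputing covariates keeps patients whom the mixed model would drop. The planned imputation is therefore worth keeping. But the plan names no auxiliary variable, and the exit interview is given when a patient finishes the study, so it may be absent for those who drop out.

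**The effect may be small.** This stands too. The 19% figure needs 40% vs 22% missing at month 12 and a shift of 0.5 SD, which is large: 0.70 to 0.82 of the residual SD given one to four other scores at correlation 0.7. At the 0.13 to 0.28 SD found in the simulation, even the heavier case gives only 2.6% to 6.2% at 4,300 and 2.0% to 3.1% at 1,500. Several modes of completion also remove one route to non-response.

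**The study is observational and disclaims causal effects of full treatment histories.** This does not answer the point, because an association over 12 months is biased in the same way.

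**Conclusion.** The concern holds in a limited form. As written, the only sensitivity check on missing data shares the mixed model's key assumption, so agreement between the two is not evidence of robustness to outcome-dependent dropout. That part rests on method alone.

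The size is a different matter. Every rate above depends on assumed dropout, correlation, group split and shift, and material bias in this study cannot be judged from the documents. A reader might infer that the primary contrasts are biased or that their error rate is badly inflated. The documents support neither: under lighter dropout the rate stays within about 2% to 6% against a nominal 1.7%, and it is nominal when missingness and shifts match across groups. The mixed model remains a reasonable primary analysis. This is a cheap and worthwhile improvement to the plan, not a demonstrated error in its results.

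**What to change.** 1. Keep the planned imputation and name its auxiliary variables: complications, treatment change and exit-interview data, all already collected.
2. Pre-specify one delta-adjusted (pattern-mixture) analysis for total Neuro-QoL and total NBSS. For each pairwise contrast, shift the imputed scores in one group at a time, in either direction, over a short fixed grid in SD units, with the other group's shift held at zero. Report the one-group shift at which the conclusion at the 0.017 level changes. Moving one group at a time matters: if shifts may vary freely in both groups there is a frontier of tipping values rather than one, and equal shifts cancel where missingness is equal.
3. Report missingness by baseline treatment group and visit, from the sent and completed dates already tracked.
4. State that agreement between the mixed model and standard imputation will not be presented as robustness to outcome-dependent dropout.

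The cost is SAP wording, modest programming and a few tables. No new data are needed and the primary analysis is unchanged. The downside is that the robustness statement may turn out less favourable.
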